6.3 Power Considerations

Power analysis is based on Specific Aim 2, as the patients enrolled therein will be a subset of the patients from Specific Aim 1. The study is powered to detect a difference in the one-year overall survival rate (i.e., the primary endpoint) between the two groups in Specific Aim 2: those patients who see a geriatrician (Group 2) and those who do not (Group 1). Based on prior observational data, overall survival in Group 1 is expected to be 68% at one year (this is based on the one-year OS of a sample of 114 MDS patients followed at DFCI from 2006 to 2012). We expect the one-year overall survival rate in Group 2 (the intervention group) to be 85%, which corresponds a 25% of improvement over Group 1. A total sample size of 160 (107 Group 1; 53 Group 2) would achieve 80% power to detect this difference, at 0.05 one-sided type I error level.

Indeed, the number of patients seen in the OHM program will be limited by the resources of the CRC and the geriatricians. In one year, given current numbers, we would expect 600 unique myeloma, lymphoma and AML/MDS patients over aged 75 (see above) to present at DFCI. We will be aiming to undertake baseline assessments for all new patients appearing on four calendar days each week. We originally hoped to have 540 potential patients for Specific Aim 1. As of December 18, 2017, 494 patients out of the 570 patients approached (87%) have agreed to Specific Aim 1. Given our line of success with enrolling patients since February 3, 2015, and after discussions with our clinicians, we hope to recruit three times the number of

patients originally planned for this aim in order to conduct disease-specific analyses. We hope to have 1,620 potential patients for Specific Aim 1 so we may stratify analyses by our three disease-specific clinics at DFCI (MDS/leukemia, lymphoma, and myeloma).

If 216 (60%) of the 540 patients, originally planned for accrual, are ultimately assessed by the CRC, and 25% found to be frail or pre-frail continue to receive care at DFCI, and agree to the RCT, this leaves 54 to be randomized to geriatric co-management vs. routine oncology care (27 in each group) per year. Our hope is to reach a sample size of 160 patients (107 Group 1; 53 Group 2) for Specific Aim 2 in three years, but we will extend the study until we achieve this enrollment. Of note, we have expanded our geriatrician clinics to two sessions per week to accommodate this increased patient load.

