3.0 OBJECTIVES/STUDY AIMS

The goal of this study is to establish a research program – the Older Adult Hematologic Malignancy (OHM) program – that will address important gaps in data about how best to care for older adults with hematologic malignancies. It is clear that markers of frailty are important predictors of tolerance of therapy and survival, but few studies have assessed their value in this population. Geriatric assessment and co-management are associated with improvements in quality of life, resource utilization and survival, but have not been tested scientifically in hematologic malignancies. We therefore propose the following specific aims:

3.1 Specific Aim 1

Characterize the prognostic value of frailty as compared to clinical prognostic models for older patients with blood cancers. We will perform a combined frailty

assessment in patients 70 and older who present to DFCI with a new diagnosis of MDS or a hematologic malignancy. Patients will be categorized as robust, pre-frail or frail based on their frailty score. We will then determine how the presence or absence of frailty predicts important outcomes such as treatment, resource utilization and mortality. In a subset of patient who specifically agree, frailty will be re-assessed at subsequent visits.

Hypothesis: Frailty will predict survival for those older patients with low-risk disease on molecular markers/disease-based risk systems, but be trumped by these for patients with high-risk disease.

3.2 Specific Aim 2

Determine if co-management of frail and pre-frail older adults with blood cancers by an embedded geriatrician improves outcomes. Patients who score as pre-frail or frail will be randomized to geriatric assessment and co-management with a geriatrician or usual care. They will be followed for disease-specific outcomes, with the primary outcome being overall survival at 1 year.

[figure not shown]
Hypothesis: For those assessed to be frail with rigorous measurement, co-management by an embedded geriatrician will improve overall survival at one year.

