5.1 Patient Selection and Recruitment

All eligible patients will be given an in-person or virtual appointment with our clinical research coordinator before their first meeting with their hematologist to discuss the study; the type of appointment will depend on availability during the COVID-19 pandemic. This CRC will have been trained in frailty assessment by [name] and will be responsible for obtaining informed consent and completing the baseline frailty assessment for patients who consent. Importantly, patients will be able to consent to the baseline assessment, a potential follow-up assessment at a future visit, and/or allowing collection of extra samples for the laboratory. Categorical frailty status (robust versus frail/pre-frail) will be emailed to clinicians.

For Specific Aim 2 (now closed to enrollment), patients will be allowed to see a geriatrician outside of the trial design if they ask for this or if their physician requests it. We acknowledge that this may somewhat affect our randomized design, however, we feel that it is important to offer this service. Frail or pre-frail patients who were not randomized to geriatric co-management but who see a geriatrician anyway will first be analyzed in an intent-to-treat manner and then excluded from a secondary analysis to assess if this event affects overall findings.

As above, frail, pre-frail and robust patients will undergo additional prospective evaluation to assess for study outcomes: for Specific Aim 1 we will compare frail and pre-frail

patients who did not see a geriatrician to robust patients, and for Specific Aim 2, we will compare frail and pre-frail patients who saw a geriatrician to those who did not (see schema).

For all patients who go on to see a geriatrician, whether inside or outside of the trial design, continued follow-up (i.e. past the initial comprehensive geriatric assessment) will be determined by discussion between the geriatrician, the patient, and the patient's DFCI oncologist. As long as this resource remains available, patients will be able to follow-up with our geriatricians as long as they continue to receive their care at DFCI.

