5.2 Registration Procedures

5.2.1 General Guidelines for DF/HCC and DF/PCC Institutions

The 166 patients who participated in the randomized control trial (Aim 1) were all entered into the Clinical Trials Management System (CTMS) OnCore per DF/HCC guidance. As of September 1, 2020, all those who participate in the observational arm (Aim 2) will be also be prospectively registered in OnCore as per DF/HCC Policy REGIST-101.

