Emergency department visits	6 months	Number of ED visits	Patient medical record and outside records
Code status documentation	6 months	Code status entered into the medical record	Patient medical record
Continuation of care at DFCI	6 months	Number of visits and length of follow-up at DFCI; receipt of treatment at DFCI	Patient medical record
Δ Number of medications	Baseline to 3 months	Overall number of medications = number of cancer meds + number of non cancer meds	Patient medical record
Δ Blood pressure	Baseline, 6 months	Measured at each visit	Patient medical record
Content Analysis of Notes	6 months	Only patients randomized to geriatrician	Patient medical record

*primary outcome

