6.0 ANALYTIC CONSIDERATIONS

6.1 Specific Aim 1

We will first perform descriptive analyses of covariates of frailty/pre-frailty in our population, including age, gender, race-ethnicity, and disease type. Means and proportions will be used to describe patient characteristics, individual and summary frailty responses, baseline clinical data, and treatment assignment. We will identify variables that are associated with the outcomes of interest using Kaplan-Meier curves and log-rank tests. Given limited numbers of patients and other study resources, we will plan to combine the frail and pre-frail groups in our analyses for Aim 1 (frail/pre-frail versus robust), but if power allows, we will also compare outcomes for all three groups (frail versus pre-frail versus robust). We will use the tests above for univariate analyses to determine whether any of the relevant geriatric domains, socio-demographic factors, or clinical data are associated with choice of treatment, length of time in the hospital and survival. We will also perform univariable and multivariable analyses to determine if frailty interacts with other patient characteristics to influence outcomes. We will also conduct analyses specific to disease clinics at DFCI (MDS/leukemia versus lymphoma versus myeloma). We will consider a p value < 0.05 to be significant, and all analyses will be carried out using SAS v.9.

6.2 Specific Aim 2

For frail patients, pre-frail patients and the combined cohort, we will create multivariable models to assess the impact of geriatric co-management on the outcomes listed in Table 3, controlling for age, gender, race-ethnicity, and disease type. We will consider a p value < 0.05 to be significant, and all analyses will be carried out using SAS v.9. Of note, we again plan to combine the frail and pre-frail groups in our analysis given limited resources and lack of current data as to whether or not geriatric intervention is more helpful in one of these groups; if power allows (see below), we will also adjust for frail versus pre-frail status.

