8.0 PROJECT TIMELINE

January 2015	Obtain OHRS approval
February 2015	Begin baseline geriatric assessments and randomization
August 2015	Interim analysis for Specific Aim 1
May 2018	Finish enrollment for Specific Aim 2
June 2018 to August 2019	Continuing enrolling participants to Specific Aim 1; Interim analyses for Specific Aim 1; Analysis and abstract write-up for Specific Aim 2
September 2019 to January 2020	Final manuscript for Specific Aim 2
February 2020 to January 2024	Continuing enrolling participants to Specific Aim 1; Interim analyses for Specific Aim 1; Continue follow-up for outcomes.
January 2024 to January 2025	Specific Aim 1 analysis; Final manuscript for Specific Aim 1

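### Does the p<0.05 rule in section 6.2, which names no side, undercut the 80% power that section 6.3 computes one-sided?

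*Combined protocol and SAP*

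**What the plan says.** Section 6.3 names one-year overall survival as the primary endpoint of Aim 2 and expects 68% in Group 1 (no geriatrician) and 85% in Group 2 (geriatrician). It states that 160 patients, split 107 and 53, "would achieve 80% power to detect this difference, at 0.05 one-sided type I error level".

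Section 6.2 describes the Aim 2 analysis as "multivariable models to assess the impact of geriatric co-management on the outcomes listed in Table 3", adjusted for age, gender, race-ethnicity and disease type. The threshold is "We will consider a p value < 0.05 to be significant, and all analyses will be carried out using SAS v.9". Section 6.1 closes with the same threshold for Aim 1. Neither section gives a side.

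The hypothesis in section 3.2 has a direction: "co-management by an embedded geriatrician will improve overall survival at one year". Table 3 in section 5.4 marks survival as the primary outcome. It also lists outcomes with no obvious favourable direction, such as code status documentation ("Code status entered into the medical record").

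**The concern.** A sample size justified at one-sided 0.05 does not carry its power over to a two-sided test at 0.05. The section that governs the analysis applies one threshold to survival and to outcomes for which a one-sided test makes little sense. A reader could therefore take p<0.05 in its usual two-sided meaning and conclude that the trial was sized for one test and analysed by another.

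Two things would be at stake:

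- **Power.** If the test were two-sided, a null result would be credited with a 20% chance of missing the planned effect when the true chance is about 25% to 35%.
- **The verdict in borderline cases.** Survival of 73/107 versus 43/53 is significant by a one-sided pooled z-test and not by a two-sided one.

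Conversely, if the test is one-sided, the chance of falsely declaring benefit is 5%, while a reader who assumed a two-sided test would infer 2.5%.

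**Working it through.** **Inputs, all from section 6.3.** p1 = 0.68, p2 = 0.85, n1 = 107, n2 = 53, one-sided level 0.05 (critical value 1.645), stated power 80%. The two-sided comparison uses 1.960. Φ is the standard normal distribution function and d = 0.85 − 0.68 = 0.17.

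**1. Reproduce the stated 80%.**

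*Unpooled z.* SE = √(0.68×0.32/107 + 0.85×0.15/53) = √(0.002034 + 0.002406) = 0.0666. Power = Φ(0.17/0.0666 − 1.645) = Φ(0.907) = 81.8%. Exact binomial enumeration of the same test gives 80.2%.

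*Arcsine.* h = 2·arcsin√0.85 − 2·arcsin√0.68 = 2.346 − 1.939 = 0.407. Power = Φ(0.407×√(107×53/160) − 1.645) = Φ(0.779) = 78.2%.

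These three figures lie within about 2 points of 80%.

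**2. Other tests.**

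*Pooled z.* The pooled rate is (107×0.68 + 53×0.85)/160 = 0.736. SE0 = √(0.736×0.264×(1/107 + 1/53)) = 0.0740. Power = Φ((0.17 − 1.645×0.0740)/0.0666) = 76.6%.

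*Log-rank (exponential survival).* HR = ln 0.85/ln 0.68 = 0.421. Expected deaths = 107×0.32 + 53×0.15 = 42.2. Power = Φ(√(42.2×0.669×0.331)×0.864 − 1.645) = 84.1%, where 0.864 = |ln 0.421|.

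**3. Replace 1.645 by 1.960.**

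| Test | One-sided 0.05 | Two-sided 0.05 |
|---|---|---|
| Unpooled z | 81.8% | 72.3% |
| Unpooled z, exact enumeration | 80.2% | 72.1% |
| Arcsine | 78.2% | 67.9% |
| Pooled z | 76.6% | 64.6% |
| Log-rank | 84.1% | 75.2% |
| Fisher exact | 71.1% | 62.0% |

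The stated 80% is matched only in the one-sided column, so the figure and the side given in section 6.3 belong together. The methods that match it give about 68% to 72% two-sided. The ends of the wider 65% to 75% range come from the pooled z and log-rank tests, which do not reproduce the plan's figure one-sided.

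**4. The borderline example.** 73/107 = 68.2% and 43/53 = 81.1%, a difference of 12.9 points. With a pooled rate of 116/160 = 0.725, SE0 = 0.0750 and z = 1.72. This gives p = 0.043 one-sided and 0.085 two-sided. Under the planned effect, the share of trials that fall between the two rules is the gap between the columns: 80.2 − 72.1 = about 8 points (exact unpooled) to 76.6 − 64.6 = 12 points (pooled).

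**5. Which side does the plan give?** Section 6.3 states one-sided 0.05 for the primary endpoint. Section 3.2 states a directional hypothesis for that endpoint. Section 6.2 uses the same 0.05, is silent on the side, and refers forward to the power section. No section mentions a two-sided test. The specific statement for the primary endpoint fills the silence in the general rule, and the two do not collide.

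**The case for a change.** The strongest opposing case is that section 6.3 is only a power statement, while the decision rule stands in section 6.2. That rule covers treatment assignment, code status and blood pressure change, where a one-sided test is not sensible, so its ordinary reading is two-sided. No sentence carries the one-sided level into the final test, and up to about 12% of trials under the planned effect would change verdict with the side.

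Part of this stands. Section 6.2 does not repeat the side, and the arithmetic behind the two-sided figures is correct. However, the lack of a favourable direction for secondary outcomes says nothing about the side of the survival test, for which the plan gives both a direction and a level. The 5% risk of falsely declaring benefit is disclosed in section 6.3, so a reader of the plan is not misled about it.

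An objector may add that an unrecorded side can look chosen after the fact. But section 6.3 does record one. Section 5.1 describes Aim 2 as closed to enrollment, section 5.2.1 counts "The 166 patients who participated in the randomized control trial", and section 8.0 schedules "Analysis and abstract write-up for Specific Aim 2" for June 2018 to August 2019. The current text already describes arrangements from September 2020, so a sentence added now would post-date the scheduled analysis. It would give no protection against a late choice and could not alter the sample size or the power.

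**Conclusion.** The concern does not call for a change. The stated 80% is not an arithmetic error: it is matched at 78.2% to 81.8% for the test that section 6.3 names. With section 6.3 governing the primary survival comparison, the plan delivers approximately its stated power at its stated 5% one-sided error rate. Section 6.2's silence is missing detail that an analyst can supply from sections 6.3 and 3.2.

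This rests on two assumptions. First, the primary test was run one-sided, as section 6.3 says. Had it been two-sided, the matching methods give about 68% to 72% power, and the 80% would not describe that analysis. Second, the figures are for unadjusted tests. The power of the covariate-adjusted model in section 6.2 cannot be computed from the documents under either reading.

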6.4 Randomization Procedures

Randomization will be stratified by general disease type (myeloma versus lymphoma versus MDS/AML). Specific procedures will include permutation block randomization in blocks of four and six to avoid predictability of intervention groups.

7.0 REGULATORY REQUIREMENTS

7.1 Informed Consent

Informed consent will be required for all patients in the study. Patients will be able to consent to the baseline assessment, a potential follow-up assessment at a future visit, and/or allowing collection of extra samples for the laboratory.

7.2 Patient Confidentiality

Subjects will be identified by their initials and study ID number only. All sensitive electronic information will be kept in a database on a secure server and will be accessed via a Partners desktop computer within DFCI or an encrypted and password protected Partners laptop. Data transfer will occur via encrypted thumb drive. In addition, the computers to be used in this project are stored in secure offices and are accessible only to authorized personnel. All sensitive paper information will be locked in a file cabinet in the principal investigator's office. All study personnel will undergo data security and confidentiality training. All data will be destroyed one year after relevant publications.

7.3 Potential Benefits of the Proposed Research

Patients may or may not benefit from this study. However, the benefit to society in this study is substantial. Discoveries made from this data will be useful to scientists, practicing physicians and individual patients. Specifically, as geriatric assessment and management have been shown to improve functional status, decrease hospitalization, and even lengthen life in non-cancer settings, we hope that our work will eventually create a more accurate prognostic model and patient-centered approach for older patients with blood cancers. The data we generate from our analysis will serve as pilot data for larger and grantable projects. In addition, we are hopeful that the creation of an infrastructure for the rapid identification and dissemination of samples to our wet lab collaborators will result in improving ongoing efforts at defining the important molecular mechanisms of hematologic cancers in the elderly, a vital future source of patient-centered care.

7.4 Importance of the Knowledge to be Gained

This study will generate valuable information about the treatment and outcomes of older patients with hematologic malignancies. This in turn will lead to improvements in the assessment and clinical care of these patients. The risk-benefit ratio is highly favorable given the potentially large societal benefits and essentially negligible risk to the participants.

8.0 PROJECT TIMELINE

January 2015	Obtain OHRS approval
February 2015	Begin baseline geriatric assessments and randomization
August 2015	Interim analysis for Specific Aim 1
May 2018	Finish enrollment for Specific Aim 2
June 2018 to August 2019	Continuing enrolling participants to Specific Aim 1; Interim analyses for Specific Aim 1; Analysis and abstract write-up for Specific Aim 2
September 2019 to January 2020	Final manuscript for Specific Aim 2
February 2020 to January 2024	Continuing enrolling participants to Specific Aim 1; Interim analyses for Specific Aim 1; Continue follow-up for outcomes.
January 2024 to January 2025	Specific Aim 1 analysis; Final manuscript for Specific Aim 1

Appendix A: Frailty Scoring Values

Cumulative Deficit Model (CDM) Variable Index and Scoring

Obtainment	Measured Variable	CDM Scoring (scaled 0-1)
Patient questionnaire	1 Bathing	With some help or completely unable=1; Without help=0
	2 Dressing	
	3 Getting in/out of chair	
	4 *Walking around house	
	5 Eating	
	6 Grooming	
	7 Using Toilet	
	8 Getting up/down Stairs	
	9 Lifting 10 lbs	
	10 Shopping	
	11 Doing housework	
	12 Meal preparations	
	13 Taking medication	
	14 Handling finances	
	15 Walk outside	<3 days=1; \geq 3 days=0
	16 Self-report ECOG PS	3-4=1; 1-2=0.5; 0=0
	17 Self rating of health	Poor=1; Fair=0.75; Good=0.5; V. Good=0.25; Excellent=0
	18 How health has changed in last year	Worse=1; Better/Same=0
	19 Stayed in bed at least half the day due to health (in last month)	Yes=1; No=0
	20 Cut down on usual activity (in last month)	
	21 *Lost more than 10 lbs in last year	
	22 **Difficulty gripping with hands	“Slow” = 1; “Steady Average” or “Fast” = 0
	23 **Self-reported walking speed	
	24 *Feel Everything is an Effort	
	25 *Have Trouble getting going	Most of time=1; Some time=0.5; Rarely=0
	26 Feel Depressed	
	27 Feel Lonely	
	28 Feel Happy	Most of time=0, Some time=0.5, Rarely=1
Patient medical record	29 High blood pressure	Yes=1; Suspect=0.5; No=0
	30 Heart attack	
	31 CHF	
	32 Stroke	
	33 Cancer	
	34 Diabetes	
	35 Arthritis	
	36 Chronic Lung Disease	

Assessed by research staff	37	BMI	See Tables below for cut points
	38	*Usual pace walk speed	
	39	*Rapid pace walk speed	
	40	MoCA 5 word delayed recall	
	41	*** Clock-in-the-box or Clock Draw	
	42	Ability to explain presentation to DFCI	
	43	Ability to complete assessment without assistance of others	“Yes” = 0; “No” = 1

* Also used in calculation of Phenotype Frailty Score

** Used in calculation of Phenotype Frailty Score if respective physical measure is not available

*** Clock-in-the-box used during in-person assessments; Clock Draw used during virtual assessments

Physical variable cut-points¹²

Variable	Deficit for Men	Deficit for Women	Source of Cut point
Body Mass Index (BMI)	<18.5, \geq 30 as a deficit. 25-<30 as a 'half deficit'	<18.5, \geq 30 as a deficit. 25-<30 as a 'half deficit'	Published ²⁹
Grip Strength (GS in kg)	For BMI \leq 24, GS \leq 29 For BMI 24.1–28, GS \leq 30 For BMI >28, GS \leq 32	For BMI \leq 23, GS \leq 17 For BMI 23.1–26, GS \leq 17.3 For BMI 26.1–29, GS \leq 18 For BMI >29, GS \leq 21	Published ^{3,26}
Rapid pace Walk	<0.61 m/s (6.56 sec)	<0.61 m/s (6.56 sec)	Published ²⁶
Usual pace Walk	<0.38 m/s (10.50 sec)	<0.38 m/s (10.50 sec)	Published ¹²

MoCA 5 word delayed recall normative data and cut-points¹⁴

Memory	Normal Control		Mild Cognitive Impairment		Alzheimer's Disease	
	AVG	SD	AVG	SD	AVG	SD
	3.73	1.27	1.17	1.47	0.52	1.03
Words Recalled Successfully	5	4	3	2	1	0
Corresponding CDM Score	0	0.25	0.5	0.75	1	1

Clock-in-the-box (CIB) normative data for age and education and cut-points²²

Age (y)	Education			
	Less than High School (SD)	High School (SD)	College (SD)	Graduate School (SD)
75-79	5.1 (1.9)	6.3 (1.6)	6.4 (1.3)	6.6 (1.4)
80-84	4.6 (1.9)	5.8 (1.5)	5.9 (1.6)	6.7 (1.2)

>85	4.9 (1.3)	5.4 (1.3)	5.8 (1.7)	6.5 (1.5)	
CIB Score	8	7	6	5	0-4
Clock Draw Score	7	6	5	4	0-3
Corresponding CDM Score	0	0.25	0.5	0.75	1

Phenotype Model Variable Index

	Index Item*	Measured Variable	Scoring
1	21	Weight loss	Yes=1, No=0
2	24,25	Self-Reported Exhaustion	Most of the time (for either) =1, some or rarely (for both) =0
3	4	Energy Expenditure	Some assistance or completely unable=1, without assistance=0
4	38,39 or 23	Gait Speed (usual and rapid pace)	IF 38, 39: Slower than cut-point=1, faster than cut-point=0 IF 23: “Slow” = 1; “Steady Average” or “Fast” = 0
5	36 or 22	Grip Strength	IF 36: Weaker than cut-point=1 (for strongest measurement), stronger than cut-point=0 IF 22: Yes = 1; No = 0

*Numbers correspond to item number in Cumulative Deficit Variable Index (above).

